4 STUDY DESIGN AND ENDPOINTS

4.1 DESCRIPTION OF THE STUDY DESIGN

ARM 1: Phase 1B

The phase IB study will consist of an accelerated titration, intrapatient dose escalation cohort, with double-dose step design. The initial single patient cohort will begin by taking 0.3mg (10mg of Verapamil in 240mL of buffered normal saline yielding an established 3% residual nasal dose) as a nasal irrigation BID for 1 week. The first dose f

each escalation will be administered in a 10th or 11th floor MEE clinic withhemodynamic monitoring. A medically trained member of the study staff with monitor the patient for one hour. Patients will be instructed on the how to properly perform the irrigation using a pre-recorded video demonstration. If no first-course dose limiting toxicity (DLT, defined by the development of 2nd or 3rd degree heart block) is noted then patients will continue taking the current Verapamil rinse dose BID for 1 week. Dose escalation will occur weekly in the absence of a single, any course, DLT or a second, any course, intermediate toxicity(IT, defined by a heart rate of <50, an asymptomatic BP reduction >30% from baseline or systolic BP <90mmHg, an asymptomatic MAP reduction >30% from baseline or MAP<55, an asymptomatic diastolic BP reduction >30% from baseline, and a Meltzer Compliance Grade >4[60]). Each escalation will be a doubling of the dose from 0.3-2.4mg. At that point that dose will escalate in 0.6mg residual intervals for the rest of the trial up to a maximum of 3.6mg total residual dose. These doses were derived from the pharmacokinetic analysis of our oral Verapamil trial results. If a single, any course, DLT or second, any course, IT occurs, two additional patients will be recruited at that identified dose and Phase IB will revert to a standard 3+3 design. If any patient un-enrolls while the dose escalation is still occurring, they will be replaced to maintain 3 patient cohorts. The maximal administered dose(MAD) will be considered that at which at least 2 DLTs or 4 ITs occur and the MTD will then be assigned to the immediate preceeding dose.

At each weekly visit, the patients nasal endoscopy will be recorded for LKS grading, and they will be administered symptom, side-effect, and tolerability questionnaires. Pre-dosing mucus and post-dosing irrigant samples will also be atraumatically collected from the nasal cavity for use in exosomal biomarker sampling.

ARM 2: Phase 2

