4.2.2 SECONDARY ENDPOINTS

Phase Ib:

Intermediate toxicity will be defined as: a heart rate of <50, an asymptomatic BP reduction >30% from baseline or SBP <90mmHg, an asymptomatic AMP reduction >30% from baseline or MAP<55, an asymptomatic DBP reduction >30% from baseline, and a Meltzer Compliance Grade >4.

Mild toxicity will be defined as a Meltzer Compliance Grade of 2-3.

Phase II:

The secondary outcomes of Phase II will be to determine the efficacy of Verapamil HCl at the MTD as measured by a subjective 10cm visual analog scale(VAS), Meltzer topical irrigation satisfaction and compliance scores, and the validated Lund-Kennedy nasal endoscopy score(LKS).

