5.4 PARTICIPANT WITHDRAWAL OR TERMINATION

5.4.1 REASONS FOR WITHDRAWAL OR TERMINATION

Arm 1: Phase 1B

The PI will terminate a Phase IB participant if they experience a DLT, more than one IT, or begin a contradictory medication during the course of the trial. Patients may withdraw from the trial at any time upon request. Any withdrawn participants from Phase IB will be replaced to maintain 3 patient cohorts. Their reason for withdrawal will be noted.

Arm 2: Phase 2

The PI will terminate a Phase II study participant if they present with any clinical adverse event (AE) or other medical complication such that continued participation in the study would not be in the best interest of the participant. The PI will terminate a participant if they miss more than 2 doses of topical Verapamil in a week. Compliance will be checked using a patient dosing diary. Participants may withdraw from the trial at any time upon request. Any withdrawn participant will be replaced with a new enrollment.

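### The intermediate-toxicity (IT) count that sets the MAD has no unit, the escalation rules disagree, and Meltzer grade 4 is in no toxicity class

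*Combined protocol and SAP*

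**What the plan says.** Section 4.1 (Arm 1) states the limit as "The maximal administered dose(MAD) will be considered that at which at least 2 DLTs or 4 ITs occur", after which "the MTD will then be assigned to the immediate preceeding dose". Finding the MTD is the Phase Ib primary endpoint (Section 4.2.1).

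An IT is given by five listed items: heart rate ("defined by a heart rate of <50"); systolic pressure ("an asymptomatic BP reduction >30% from baseline or systolic BP <90mmHg"); mean and diastolic pressure ("an asymptomatic MAP reduction >30% from baseline or MAP<55, an asymptomatic diastolic BP reduction >30% from baseline"); and the Meltzer item ("and a Meltzer Compliance Grade >4" in Section 4.2.2, with the same cut-off in 4.1 and the synopsis). Section 4.2.2 adds a lower class: "Mild toxicity will be defined as a Meltzer Compliance Grade of 2-3".

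The same count drives other rules. In 4.1, a second IT on any course stops the single-patient escalation and brings in two more patients under a 3+3 design. Section 5.4.1 says: "The PI will terminate a Phase IB participant if they experience a DLT, more than one IT". Section 6.1.8 bars escalation for a participant with a DLT or two ITs on the preceding dose. Section 7.3.3 provides for moving up when the participant has had neither an IT nor a DLT.

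**The concern.** A toxicity limit works only if two people with the same case report forms reach the same count. Here three of the five IT items are functions of one cuff reading, and nothing says whether items met together are one IT or several. The documents also do not say whether the limit refers to people or to events.

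The MTD is the dose just below the MAD, and 4.1 carries it into Phase II. (Section 6.1.5 names the MAD as the Phase II dose, a discrepancy to be reconciled in its own right; on either text the MAD call decides what Phase II participants receive.) An unsettled count therefore leaves the Phase Ib primary result open to a choice made after the data are seen. It also affects who is removed from treatment and when the cohort expands.

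**Working it through.** The plan gives no target toxicity rate, operating characteristic or worked count for this limit, so there is no stated figure to reproduce.

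**Inputs.** IT items, MAD limit and cohort of three (one patient plus two): Section 4.1. Baseline pressure of at least 110 systolic and 70 diastolic: Section 5.2. Assumed: MAP = (SBP + 2 × DBP)/3, and an illustrative asymptomatic fall from 120/80 to 80/50.

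**Step 1: the items overlap.**
- SBP: (120 − 80)/120 = 33.3%
- DBP: (80 − 50)/80 = 37.5%
- MAP: (120 + 160)/3 = 93.3 falls to (80 + 100)/3 = 60; (93.3 − 60)/93.3 = 35.7%

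This does not depend on the MAP formula. If SBP and DBP each end below 0.7 of baseline, so does any weighted average of them. For a baseline SBP under 90/0.7 = 128.6, a systolic fall of more than 30% also takes SBP below 90.

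**Step 2: what this reading scores.**

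| Unit | Pressure alone | With heart rate <50 |
|---|---|---|
| Participant or episode | 1 | 1 |
| Listed item | 3 | 4 |
| Separate threshold | 4 | 5 |

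The four thresholds are SBP down more than 30%, SBP below 90, MAP down more than 30% and DBP down more than 30%; MAP of 60 is not below 55. A deeper fall, 120/80 to 75/42 (MAP 53), meets all five pressure thresholds but still three items. A fall from 140/90 to 97/62 meets three of each.

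**Step 3: the rules applied to the pressure fall alone.**
- Second-IT trigger (4.1) and removal for more than one IT (5.4.1): met by item (3) or threshold (4), not by episode (1).
- MAD limit of 4: met by threshold, one short by item, not met by episode.
- One IT in each of three participants: 3 in total, below 4.

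**Step 4: how much the unit matters.** Let p be the chance that a participant has one such fall at a dose (assumed), with one episode per affected participant. The chance of reaching 4 ITs is:

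| Unit | Needed | p = 0.10 | p = 0.20 | p = 1/3 |
|---|---|---|---|---|
| Threshold (4 each) | 1 of 3: 1 − (1 − p)³ | 0.271 | 0.488 | 0.704 |
| Listed item (3 each) | 2 of 3: 3p²(1 − p) + p³ | 0.028 | 0.104 | 0.259 |
| Participant | 4 of 3 | 0 | 0 | 0 |
| Participant, six treated | 4 of 6 | 0.001 | 0.017 | 0.100 |

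**Step 5: the escalation rules side by side.**

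| Participant's history | 4.1 | 6.1.8 | 7.3.3 |
|---|---|---|---|
| One IT ever, on the dose just completed | may escalate | may escalate | condition for moving up not met |
| One IT on an earlier dose, one on the dose just completed | stops | may escalate | condition for moving up not met |

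The second row can arise only if 7.3.3 was not applied after the first IT. In that row 5.4.1 would also remove the participant.

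**Step 6: Meltzer grade.** Mild covers 2 and 3, and an IT starts above 4. Grade 4 meets neither definition, so as written it is recorded as no toxicity although it lies between the two classes.

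**The case against.** The best reply is that 4.1 treats an IT as one toxicity with a list of qualifying signs, and that its references to first-course and any-course events point to counting by course. On that reading one cuff reading is one IT, and the overlap does no harm. This is a fair reading and may be what was meant. But the MAD sentence does not say so, and Section 8.1 lists the pressure criteria as separate safety parameters that are also Phase Ib endpoints, so counting by criterion is open too.

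The reply is right against several stronger readings that a reader might infer:

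- That the plan double-counts. It does not say that; it is silent.
- That a pressure fall alone in one participant sets the MAD. By listed item it scores 3. It reaches 4 only with heart rate below 50, with the two halves of an 'or' item split, or with repeat readings counted.
- That 4 can never be reached by participant. That holds for three people. Under a 3+3 design six may be treated, and withdrawn participants are replaced.
- That escalation would go past a dose at which all three had an IT. Not reaching the MAD is not the same as escalating: 4.1 stops at a second IT, and 7.3.3 provides for moving up only without any. The defect is that these conditions and 6.1.8 disagree.
- That the Meltzer gap distorts the MAD. Grade 4 is clearly not an IT, and mild toxicity enters no escalation or MAD rule. The gap is a separate fault in classification.

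**Conclusion.** The point holds in this form: the IT rules do not yield one answer from one set of observations. A single pressure fall can score 1, 3, or 4 or more ITs, and by listed item it at once meets both the second-IT trigger and the removal rule. With three participants and an assumed 20% chance of such a fall, the probability of reaching the limit is 0.488, 0.104 or 0 depending only on the unit. Those probabilities rest on assumed values of p, on one episode per affected participant and, for the threshold count, on a fall that meets at least four thresholds. The overlap of the three pressure items, the conflict between 4.1, 6.1.8 and 7.3.3, and the unclassified Meltzer grade need no such assumptions. The documents do not show which count the site would use, so neither a MAD called too early nor one called too late can be predicted.

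**What to change.** Before enrolment, the sponsor should:

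1. State in Section 4.1 one counting unit for ITs, and how criteria met at the same assessment are counted.
2. Reconcile with that unit the figure 4 in the MAD rule, the second-IT trigger in 4.1, the removal rule in 5.4.1 and the escalation conditions in 6.1.8 and 7.3.3, so that all give the same result for the same history. Say also whether ITs in replaced participants still count.
3. Assign Meltzer grade 4 to a class, consistently in the synopsis, 4.1 and 4.2.2.

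The unit, the number and the class are for the sponsor to choose. The cost is a few sentences and no new data; the one downside is that the sponsor must commit to a counting rule in advance.

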> dose step design. Participants will administer each dose Verapamil HCl dose intranasally BID. Weekly visits will occur for side-effect and escalation evaluations. Phase II will be an open label trial of 20 participants. The MTD determined in Phase Ib will be administered BID for 4 weeks.

Participants will be seen at baseline, 1 week, and 4 week for efficacy and side-effect

evaluations.

Objectives: Primary Objectives:

> -Perform a Phase IB trial of topical intranasal Verapamil HCl BID to determine the Maximal Tolerated Dose(MTD) using an accelerated titration design with intra-patient dose escalation. -Perform a Phase II trial of topical intranasal Verapamil HCl BID based on the Phase I MTD to determine safety and efficacy using both subjective and objective outcome measures of CRS. Secondary Objective:

-Determine whether mucus derived exosomal P-gp can be used as a non-invasive biomarker of CRS by correlating it with baseline symptoms of CRSwNP and treatment response to topical

Verapamil HCl at the MTD. **Endpoint**

Primary Endpoints:

Phase Ib: Defining the Maximal Tolerated Dose(MTD) of topical Verapamil HCl. DLT will be defined as a development of 2nd or 3rd degree heart block as measured by an EKG.

Phase II: determining the efficacy of topical Verapamil HCl at the MTD for subjective symptoms

of CRSwNP using the validated SNOT-22.

Secondary Endpoints:

Phase Ib: Intermediate toxicity will be defined as: a heart rate of <50, an asymptomatic BP reduction >30% from baseline or SBP <90mmHg, an asymptomatic AMP reduction >30% from baseline or MAP<55, an asymptomatic DBP reduction >30% from baseline, and a Meltzer Compliance Grade >4.

Phase II: to determine the efficacy of Verapamil HCl at the MTD as measured by a subjective 10cm visual analog scale(VAS), Meltzer topical irrigation satisfaction and compliance scores, and the validated Lund-Kennedy nasal endoscopy score(LKS).

Population: 20-40 MEE Sinus Center patients over the age of 18 who present with chronic

rhinosinusitis with polyps.

Phase: IB/II
Number of 1

Sites enrolling participants:

Description Verapamil HCl 0.3mg-3.6mg final dose BID in buffered normal saline as a nasal

of Study irrigation.

Agent:

[figure not shown]
Study December 2016 – December 2018

Duration:

[figure not shown]
Participant 1 month

Duration:

SCHEMATIC OF STUDY DESIGN

Legend				
IC	Informed Consent			
IF	Intake Form			
PT	Pregnancy Test			
SNOT-22	Sino-Nasal Outcome Test			
VAS	Visual Analogue Scale			

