3 OBJECTIVES AND PURPOSE

Primary Objectives:

- Perform a Phase IB trial of topical intranasal Verapamil HCl BID to determine the Maximal Tolerated Dose(MTD) using an accelerated titration design with intra-patient dose escalation.
- Perform a Phase II trial of topical intranasal Verapamil HCl BID based on the MTD to determine safety and efficacy using both subjective and objective outcome measures of CRS.

Secondary Objective:

- Determine whether mucus derived exosomal P-gp can be used as a non-invasive biomarker of CRS by correlating it with baseline symptoms of CRSwNP and treatment response to topical Verapamil HCl at the MTD.

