The Phase II study will be an open label safety and efficacy expansion cohort using the MTD determined in the Phase IB arm. A total of 20 patients will be administered the MTD of topical Verapamil HCl in a 240mL buffered normal nasal rinse for 4 weeks BID. This sample size was calculated based on a power analysis derived from the results of our oral Verapamil trial. The first dose will be administered in in a 10th or 11th floor MEE clinic withhemodynamic monitoring. A medically trained member of the study staff with monitor the patient for one hour. Patients will be instructed on the how to properly perform the irrigation using a pre-recorded video demonstration. If no first-course DLT occurs then patients will continue taking the topical Verapamil dose BID. Patients will then return for follow-up visits at 1 week and 4 weeks. Subjective and objective outcome measures will be collected at each visit.

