4.2.1 PRIMARY ENDPOINT

Phase Ib:

The primary outcome measurement for Phase IB(SA1) will be defining the Maximal Tolerated Dose(MTD) of topical Verapamil HCl. Dose Limiting Toxicity will be defined as a development of 2nd or 3rd degree heart block as measured by an EKG.

Phase II:

The primary outcome for Phase II(SA2) will be determining the efficacy of topical Verapamil HCl at the MTD for subjective symptoms of CRSwNP using the validated SNOT-22.

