6.1.5 DOSING AND ADMINISTRATION

Phase Ib:

Phase Ib participants will receive dosing according to the included escalation schedule. Dosing will go from an initial 0.3-3.6mg total residual dose of Verapamil HCl. Phase II Participants will receive the MAD determined by Phase Ib. Participants will administer the irrigation BID. A video demonstration on proper administration of the irrigation will be shown at the initial study visit.

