6.1.7 STARTING DOSE AND DOSE ESCALATION SCHEDULE

Phase Ib Verapamil HCl dose will start at a total residual dose of 0.3mg. Dose escalations will be as follows: 0.3mg, 0.6mg, 1.2mg, 2.4mg, 3.0mg, 3.6mg. Participants will remain on a dose for at least one week before escalating.

Phase II dose will be determined by Phase Ib.

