10.4.7 PLANNED INTERIM ANALYSES

10.4.7.1 SAFETY REVIEW

Phase Ib:

This arm will be halted when the MTD has been determined. The proposed safety endpoints will be monitored at each weekly visit. Participants will be formally queried for medication related side effects and will undergo an EKG at each visit, which will be assessed by a medical internist/anesthesiologist.

Phase II:

This arm will be halted if 20% of the population experiences a severe adverse event. This decision will be made at the discretion of the DSMB. Safety endpoints will be monitored at each of the 3 study visits (baseline, week 1, week 4). Participants will be formally queried for medication related side effects and will undergo a repeat EKG at the week 1 visit, which will be assessed by a medical internist/anesthesiologist.

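### Section 6.1.5 gives Phase II the MAD where the rest of the protocol gives the MTD, and the only MTD rule returns no clear answer if 3.6 mg is completed without the toxicity count

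*Combined protocol and SAP*

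**What the plan says.** Section 4.1 (Phase 1B) contains the only rule that produces an MTD. The MAD is the dose "at which at least 2 DLTs or 4 ITs occur and the MTD will then be assigned to the immediate preceeding dose". The same section caps escalation at 3.6 mg residual, and section 6.1.7 gives the ladder: "Dose escalations will be as follows: 0.3mg, 0.6mg, 1.2mg, 2.4mg, 3.0mg, 3.6mg".

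Four places tie Phase II to the MTD:

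- Protocol Summary: "The MTD determined in Phase Ib will be administered BID for 4 weeks".
- Section 3: a "Phase II trial of topical intranasal Verapamil HCl BID based on the MTD".
- Section 4.1 (Phase 2): "A total of 20 patients will be administered the MTD of topical Verapamil HCl".
- Section 4.2.1, where the Phase II primary outcome is efficacy at the MTD.

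Section 6.1.5 says something different: "Phase II Participants will receive the MAD determined by Phase Ib". Section 6.1.7 names no level for Phase II and leaves it to the outcome of Phase Ib.

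The MTD also carries the Phase Ib result. Section 4.2.1: "The primary outcome measurement for Phase IB(SA1) will be defining the Maximal Tolerated Dose(MTD) of topical Verapamil HCl". Section 10.4.7.1: "This arm will be halted when the MTD has been determined". Section 7.3.4 lists reaching the maximal administered dose as one of the ways a Phase Ib participant finishes, without saying whether that means the dose that met the toxicity count or simply the top dose given.

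**The concern.** Two separate things can go wrong, on two different paths.

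If a MAD is observed, the operative dosing section points Phase II at the dose that produced at least 2 DLTs or 4 ITs, one level above the dose that four other places require. The drug is cardioactive and the DLT is second- or third-degree heart block. Section 6.1.8 fixes the Phase II dose for the four weeks, and the schedule of events has no Phase II EKG after Day 7, so a wrong starting dose would not be corrected by titration.

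If no MAD is observed by the end of the 3.6 mg level, the rule has nothing to step down from. The Phase Ib primary outcome then has no defined value, and the investigators would have to choose a label after seeing the data. Nothing stops the Phase II results from being reported as obtained at the MTD when none was observed.

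**Working it through.** The plan states no figure on this point. The check is a trace of the decision rule over the ladder.

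**Inputs.** Ladder from section 6.1.7: 0.3, 0.6, 1.2, 2.4, 3.0 and 3.6 mg residual. MAD and MTD rule from section 4.1. Residual fraction 3% from section 4.1 (10 mg in the bottle gives 0.3 mg), so bottle dose = residual / 0.03.

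**Path A: a MAD is observed.** The MTD is the level below it. Section 6.1.5 read literally gives the MAD, so the ratio of the two readings is MAD / MTD.

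| MAD (mg) | MTD (mg) | MAD / MTD | Bottle dose, MTD to MAD (mg) | Extra per bottle (mg) |
|---|---|---|---|---|
| 0.6 | 0.3 | 2.0 | 10 to 20 | 10 |
| 1.2 | 0.6 | 2.0 | 20 to 40 | 20 |
| 2.4 | 1.2 | 2.0 | 40 to 80 | 40 |
| 3.0 | 2.4 | 1.25 | 80 to 100 | 20 |
| 3.6 | 3.0 | 1.2 | 100 to 120 | 20 |

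The rule can return 0.3, 0.6, 1.2, 2.4 or 3.0 mg, which is five of the six levels. It can never return 3.6 mg, because no higher level exists to be the MAD.

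**Path B: 3.6 mg is completed without 2 DLTs or 4 ITs.** The text allows three answers:

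- MAD as section 4.1 defines it: none exists, so there is no MTD and section 6.1.5 has no dose either.
- MAD as the highest dose given, a possible sense in section 7.3.4: MAD = 3.6 mg, so the step-down rule gives MTD = 3.0 mg although 3.6 mg was tolerated.
- The same sense applied to section 6.1.5: Phase II receives 3.6 mg, but sections 4.1 and 4.2.1 still call the Phase II dose the MTD.

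**How often Path B occurs.** The documents give no DLT or IT rates, so this part rests on assumption. With a DLT probability p at each dose, one patient passes all six with probability (1 - p)^6: 0.94, 0.74, 0.53 and 0.26 at p = 1%, 5%, 10% and 20%. A simulation of 100,000 trials per setting counted DLTs only. One patient escalates, the first DLT opens 3+3, and at least 2 DLTs at a level make it the MAD. The top was passed with no MAD in about 99.7%, 92%, 74% and 36% of trials at those rates, and in about 80% with rates rising 1, 2, 4, 8, 12, 16% over the ladder. ITs can also produce a MAD and were left out, so these figures overstate the frequency of Path B. They show only that it cannot be dismissed.

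**MAD at 0.3 mg.** There is no preceding dose. On the DLT route under 3+3, 2 DLTs in 3 to 6 patients is 2/3 = 67% to 2/6 = 33%, above the 20% adverse event rate at which section 8.5 halts dosing. Only a closing statement is missing.

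**The case against.** The best defence is that section 6.1.5 uses MAD in its plain sense, the highest dose given. On that reading it is not an overdose instruction. It may even supply the missing default: with no toxicity count, Phase II takes 3.6 mg. This reading is possible, and it is why the finding is a contradiction in terms and not proof of an intended overdose. It does not remove the problem, because section 4.1 defines MAD by toxicity, and the same word cannot mean both without changing the dose.

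A second defence is that the MTD is named in four other places, so section 6.1.5 is probably a slip that DSMB review (sections 8.6 and 9) and the halting rule in section 8.5 would make unlikely to be acted on. That stands as to likelihood. It does not justify leaving the error in the section that governs dosing.

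A reader might infer more than the documents support:

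- *Both harms together.* They exclude each other. One needs a MAD and the other needs none.
- *Escalation has no end.* The 3.6 mg cap still ends it, whatever section 10.4.7.1 says about the MTD.
- *The Phase II analysis fails.* The hypotheses and the sample size (20 patients, difference 15.9, SD 24) do not use the dose. The visit numbering in section 10.4.10 also works without an MTD.
- *Path B is the expected result.* The cap is only 3.6/72.75 = 5% to 3.6/16.8 = 21% of the intranasal dose that section 2.1 equates with the oral regimen. That comparison concerns systemic exposure and says nothing about ITs reached through the Meltzer compliance grade.

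The design schematic and some front pages were not available to read, so a fallback rule there cannot be fully excluded. Nothing in the readable text points to one.

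**Conclusion.** The point holds in two alternative parts. If a MAD is observed, section 6.1.5 contradicts the Protocol Summary and sections 3, 4.1 and 4.2.1, and taken literally it gives Phase II 1.2 to 2 times the MTD. This assumes section 4.1's definition of MAD applies in section 6.1.5. If 3.6 mg is completed without the count, the only MTD rule gives no MTD, or 3.0 mg under the other sense of MAD. The Phase Ib primary outcome, the halting condition in section 10.4.7.1 and the Phase II dose label are then undefined or ambiguous. The probability of that path is unknown from the documents. The 0.3 mg case is a minor clarification. The ladder arithmetic is exact and confidence in the conflict is high. Confidence that no fallback rule exists is limited to the text that could be read.

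**What to change.** 1. Section 6.1.5: replace MAD with *the MTD, or 3.6 mg if no MAD is observed*.
2. Sections 4.1 (Phase 1B) and 10.4.7.1: state that completing 3.6 mg without the MAD count ends Phase Ib as *MTD not reached; highest tested dose 3.6 mg*. Report the number of patients treated at 3.6 mg, and have the DSMB review those data before Phase II opens. The number matters because extra patients are recruited only after a DLT or a second IT, so few may have received the top dose.
3. Protocol Summary and sections 3, 4.1 (Phase 2), 4.2.1 and 6.1.7: describe Phase II as *at the MTD or, if not reached, at 3.6 mg*. Section 4.2.2 needs the same words.
4. Use MAD only as section 4.1 defines it. If section 7.3.4 means the top of the ladder, write *complete the 3.6 mg dose*.
5. State that a MAD at 0.3 mg means no tolerated dose and that Phase II does not open.

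The cost is wording plus one review by a board that already exists. No patients or visits are added, and the Phase II sample size stays at 20. The downside is a less favourable label if the cap is reached. The label itself adds no safety information at 3.6 mg, which is why the count and the DSMB review go with it.

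### Read literally, section 4.1 can name as MTD a dose that only one titrated participant has taken, for as little as one week, and this does not fit its own 3+3 wording

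*Combined protocol and SAP*

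**What the plan says.** Section 4.1 (Arm 1, Phase 1B) puts the dose-finding rule in one paragraph. It starts with one person: "The initial single patient cohort will begin by taking 0.3mg". The step-up condition is: "Dose escalation will occur weekly in the absence of a single, any course, DLT or a second, any course, intermediate toxicity". Section 6.1.7 sets the minimum exposure: "Participants will remain on a dose for at least one week before escalating". When a trigger toxicity occurs, "two additional patients will be recruited at that identified dose and Phase IB will revert to a standard 3+3 design". Of participants who leave during escalation it says "they will be replaced to maintain 3 patient cohorts". The MAD is the dose with at least two DLTs or four intermediate toxicities (ITs), and "the MTD will then be assigned to the immediate preceeding dose".

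For Arm 2, "A total of 20 patients will be administered the MTD of topical Verapamil HCl", twice daily for four weeks. Section 6.1.8 keeps the Phase II dose unchanged throughout. Section 4.2.1 makes the MTD the primary endpoint of Phase Ib.

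The available text sets no minimum number treated at the MTD and sends no participants back to the preceding dose before it is named. The replacement rules (sections 4.1, 5.4.1 and 5.4.2) and the DSMB reviews (section 9) add nobody there.

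**The concern.** The two extra participants go to the dose that caused trouble, while the dose carried into Phase II is the one below it. If the triggering dose becomes the MAD, the MTD sentence selects a dose whose whole record may be the index participant. That person reached it through lower doses and may have taken it for one week. Phase II participants begin on it directly and stay on it for four weeks, and the DLT in question is second or third degree heart block.

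The same paragraph says that the trial has by then become a standard 3+3. Staff who follow the MTD sentence and staff who read a lower-dose cohort into the 3+3 wording could act differently at the same point in the trial.

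**Working it through.** **The plan's own figures.** The documents give no operating characteristics for the dose-finding rule and no DLT rates, so there is nothing to reproduce for the rule itself. The Phase II size does reproduce. A paired t-test with difference 15.9, SD 24, two-sided 5% (sidedness is not stated) and n = 20 has noncentrality 15.9/24 × √20 = 2.96 and power 80.2%. That number is not in dispute.

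**Walking through the rule.** Suppose the index participant clears 0.3, 0.6 and 1.2 mg and has a DLT at 2.4 mg. Two participants are added at 2.4 mg and one has a DLT. There are now two DLTs at 2.4 mg, so it is the MAD and 1.2 mg is the MTD. If the added participants start at 2.4 mg, one person has taken 1.2 mg.

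Suppose instead that 2.4 mg clears its cohort and a later dose becomes the MAD. The MTD then rests on 3 to 6 participants.

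**How often the triggering dose becomes the MAD.** Let p be the assumed true DLT rate at the triggering dose. Given the index DLT, at least one more DLT is needed. The probability is 1 − (1 − p)² with two added participants, and 1 − (1 − p)⁵ if three more follow a 1/3 result, as is usual in a 3+3:
- p = 10%: 19% and 41%
- p = 20%: 36% and 67%
- p = 30%: 51% and 83%

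The rule was also simulated under four assumed dose-toxicity curves, counting DLTs only, with added participants starting at the triggering dose. Of the trials that reached an MTD by the rule, 75% to 80% had one participant treated at it. The share of trials that reached an MTD at all ran from 6% to 89%, depending on the curve.

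**What no DLT in n participants shows.** The exact one-sided 95% upper bound is 1 − 0.05^(1/n):
- 0/1: 1 − 0.05 = 95%
- 0/3: 1 − 0.368 = 63%
- 0/6: 1 − 0.607 = 39%

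**Probability that a dose passes.** For one participant this is q = 1 − p. For a rule of 0/3, or at most 1/6 after expansion, it is q³ + 3pq² × q³. At p = 30%, for example, 0.343 + 0.441 × 0.343 = 0.494.

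| Assumed true DLT rate | One participant | 0/3 or at most 1/6 |
|---|---|---|
| 5% | 95% | 97% |
| 10% | 90% | 91% |
| 20% | 80% | 71% |
| 30% | 70% | 49% |
| 40% | 60% | 31% |

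At 10% or below the cohort rule is no stricter. The difference appears at 20% and above.

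**Texts that pull the other way.** Section 6.1.7 gives one schedule for Phase Ib, starting at 0.3 mg, and section 6.1.5 says Phase Ib participants are dosed according to the escalation schedule. If this covers the added participants, they pass through the preceding dose, and the two of them with the index participant would make three there. Section 4.1 places their recruitment at the triggering dose. The documents do not settle which is meant.

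**The case against.** The strongest reply is that the outcome depends on a reading. A standard 3+3 may be meant to include testing the lower dose, and sections 6.1.5 and 6.1.7 may mean that added participants titrate. This stands in part. It is why a reader who inferred a flat contradiction, or that the MTD must rest on one person, would go beyond the documents. The 3+3 design is never defined, and the three-patient cohorts are mentioned only in the replacement rules, which fit three participants at the triggering dose. It does not remove the gap, because the one explicit MTD sentence assigns the preceding dose directly and nothing else states a condition.

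A second reply concerns size. All DLT rates here are assumed. Passing is also not the same as being named MTD, which further needs two DLTs or four ITs at the next dose. The IT trigger can stop escalation without any DLT. All of this stands.

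A reader might also infer 6 or 8 DLTs among the 20 Phase II participants (20 × 30% or 20 × 40%). The documents do not support that forecast. They give no such rates, and the counts ignore the halting rules in sections 8.5 and 10.4.7.1 and the DSMB review at 10 participants in section 9.

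Finally, Phase II is itself described as a safety and efficacy expansion. It has a monitored first dose with EKGs before and after, and an EKG at week 1. These limit harm, but they act after exposure has begun and do not supply evidence before the dose is chosen.

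**Conclusion.** The point holds as a gap in the stated rule. Followed literally, section 4.1 can yield an MTD supported by one titrated participant with at least one week of exposure, where an upper bound of 95% on DLT risk says almost nothing. Three or six event-free participants would give 63% or 39%.

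The result requires that the triggering dose becomes the MAD and that added participants do not pass through the preceding dose. The first is a likely path under moderate assumed DLT rates, and the second is unresolved in the text. The advantage of a cohort rule in screening out a toxic dose depends on the true rate: none to speak of at 5% to 10%, and 49% against 70% passing at 30%. Since the MTD is the Phase Ib primary endpoint and the fixed Phase II dose, the text should be settled before Phase II opens.

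**What to change.** The sponsor and DSMB should reconcile the MTD sentence in section 4.1 with that paragraph's 3+3 wording and with sections 6.1.5 and 6.1.7. The amended text should state whether and how the dose named MTD is itself evaluated in a cohort, and whether added participants start at the triggering dose or titrate to it. The rule, cohort size and limits are theirs to set. Section 6.1.5 also says Phase II receives the MAD where section 4.1 says the MTD, and the same amendment should reconcile these.

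The report should give the number treated at the MTD, their time on it, and an exact upper confidence bound on the DLT rate.

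The cost is one amended paragraph and possibly a few more Phase Ib participants and weeks. The Protocol Summary plans for "20-40 MEE Sinus Center patients over the age of 18", which appears to leave up to 20 outside Phase II (40 − 20). That margin is not assured, because sections 5.4.1 and 5.4.2 replace every withdrawn Phase II participant without a cap.
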